10.1. Risk Assessment

Using the LSHTM 'Monitoring Risk Assessment' tool, the CI has determined studies of this kind to be "low-risk". Day-to-day monitoring will be carried out at the study centre by a member of the study team with delegated responsibility.

Safety information regarding the repellent used in the trial have been assessed, material and safety data sheets (MSDS) and labels have been read to be sure they are safe for human use. The active ingredient in the repellent to be tested is PMD or Picaridin. Participants will be given an information sheet explaining the details of the ingredients and what to do if they have a reaction to the products or the midges after completion of the test.

10.2. Adverse events

Volunteers will be monitored throughout the duration of the tests by investigational staff for any adverse events. If any adverse events related to insect bites or the repellent products are apparent at any time during the trial, testing will stop immediately and details of how to access treatment will be offered. Volunteers can only participate in a test a minimum of 72 hours after the screening bite test and participants with known allergies to any of the product ingredients will not be eligible to take part.

Within 72 hours after laboratory testing an email will be sent to participants asking them to report any adverse events that might have occurred since the end of testing.

Adverse events that occur >72 hours after the end of participation in the trial will be passively monitored.

An adverse event which is ongoing at the time of participant withdrawal or completion will be followed up until it resolves or until 30 days after the participant terminates from the study, whichever comes first.

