3.2. Risks and Benefits

3.2.1. Midges

Participants will be exposed to insect bites and may experience some irritation and itching. The midges are reared in insectaries and have been in culture for many years and are pathogen free. In order to minimise the risk of infection the following steps have been taken:

- Midges used in the test are 3-8 days old and have never had a blood meal.
- One cage of midges is used on one volunteer only and after the test, those midges are destroyed. Therefore, no two volunteers are ever bitten by the same midges and the midges are never returned to the colony.
- There will be a minimum of 72 hours between product tests in order to minimise any possibility for sensitization to midges bites

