4.1. Screening Procedures

Volunteers will be consented prior to any screening procedures being undertaken. Volunteers who do not meet the criteria for eligibility will be excluded. In order to assess sensitivity in those volunteers who claim not to be sensitive to insect bites, volunteers will be given a bite test using the midge species used for testing. This will involve administering one *C. nubeculosus* bite and monitoring the reaction to the bite for up to 72 hours. Volunteers whose reaction (area of wheal) is larger than 1 cm, or if the participant scores their itchiness or redness as 3 out of 3 (with "1" being "no itchiness/redness", "2" being "some itchiness/redness", and "3" being "very itchy/red"), they will be unable to test with that midge species. Volunteers who fail the screening procedures will be advised that they will not proceed in the study and will be withdrawn and replaced.

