4.2. Inclusion Criteria

Volunteers will be healthy individuals and chosen based on their insensitivity to the bites in order to limit any itchiness or discomfort.

Volunteers will be included in the study if they meet all of the following criteria:

- Able and willing to give fully informed consent;
- Able to understand and comply with the study procedures;
- Consider themselves to be in good general health;
- Male or female;
- Aged 18 to 65 years;
- Non-smokers or willing to refrain for 12 hours prior to and during each test;
- Willing to undergo a bite test with *C. nubeculosus* midges with up to 72 hour follow-up.

Volunteers will be advised not to apply any cosmetics associated with a strong scent, such as perfume, hand cream, body wash, or scented. Additionally, volunteers will be asked not to drink alcohol or consume spicy foods, i.e. curries, chillies and garlic and to not to engage in vigorous exercise for the 12 hours prior to the tests. This will be verified with the participants prior to the commencement of any tests.

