7.1. Definitions

Term	Definition
Adverse Event (AE)	Any untoward medical occurrence in a patient or study participant
Serious Adverse Event (SAE)	A serious event is any untoward medical occurrence that: Results in death Is life-threatening Requires inpatient hospitalisation or prolongation of existing hospitalisation Results in persistent or significant disability/incapacity Consists of a congenital anomaly or birth defect Other 'important medical events' may also be considered serious if they jeopardise the participant or require an intervention to prevent one of the above consequences.

Medical judgement should be exercised in deciding whether an AE is serious in other situations. Important AEs that are not immediately life-threatening or do not result in death or hospitalisation but may jeopardise the participant or may require intervention to prevent one of the other outcomes listed in the definition above, should also be considered serious.

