7.2.1. Non serious AEs

All adverse events should be recorded on the Adverse Event Record Form (Appendix 1) and Adverse Event Monitoring Questionnaire (Appendix 2) and entered into a spreadsheet and stored on the "I" drive with access limited to the *arctec* study staff. All adverse events will be reported to NEO-INNOVA HEALTHCARE LIMITED. Depending on the nature of the event the reporting procedures below should be followed, see Appendix 3 for a flowchart of safety reporting.

In the event of minor adverse reactions such as localised skin redness and swelling, volunteers will be directed to contact the nearby GP surgery at [name] ([contact]) or their own GP.

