8.1. Midge Fitness Check and control test (combined)

Before the start of each test, the participant will insert a bare (control) left arm into the cage for 1 minute to assess biting activity of the midges. Only cages with at least 10 midges landing within one minute will be used in the tests. This same procedure is used to assess whether volunteers are attractive to the midges. The number of midges probing or biting the arm after 1 minute will be counted and recorded (to provide biting rate data of the control test for the Protective Efficacy endpoint) and the arm removed from the cage.

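### Section 10.2 stops testing for any bite- or product-related adverse event, which conflicts with reactions foreseen or accepted in 3.2.1, 4.1 and 7.2.1 and could end an unknown, possibly large, share of tests before CPT, with no analysis rule for stopped tests

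*Combined protocol and SAP*

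**What the plan says.** The stopping rule is in Section 10.2: "If any adverse events related to insect bites or the repellent products are apparent at any time during the trial, testing will stop immediately". It has no threshold for severity or expectedness. Section 7.1 defines an adverse event broadly, as "Any untoward medical occurrence in a patient or study participant", with no exemption for ordinary bite reactions.

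Other sections treat mild local reactions differently:

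- Section 3.2.1: "Participants will be exposed to insect bites and may experience some irritation and itching".
- Section 4.1 gives each volunteer one test bite. It excludes those with a wheal above 1 cm and anyone who "scores their itchiness or redness as 3 out of 3". The middle score, some itch or redness, is accepted.
- Section 7.2.1, on non-serious events: "In the event of minor adverse reactions such as localised skin redness and swelling, volunteers will be directed to contact the nearby GP surgery" or their own GP. Stopping the test is not mentioned.

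On exposure, Section 8.1 states: "Only cages with at least 10 midges landing within one minute will be used in the tests". Section 8.3 puts the untreated left arm in the cage at the start and then hourly, each time just before the treated arm. Section 8.4 continues until 50% protective efficacy or 12 h.

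On analysis, Section 9.2 uses Kaplan-Meier for the median CPT and linear regression to compare mean CPT. The synopsis names a two-way analysis of variance or linear model for that comparison. Section 4.4 keeps data collected up to withdrawal. None of these says how a test stopped under 10.2 enters the analysis.

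**The concern.** Read literally, a reaction that is acceptable at screening becomes a reason to stop once testing starts. The bites concerned fall mainly on the untreated arm, so a stop may say little about whether the product still works. Section 10.2 also leaves open whether a stop ends that day's session or all participation; Section 4.4 makes removal a matter for the Chief Investigator's discretion.

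The primary endpoint is exposed in two ways.

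- **Loss of information.** A test stopped before CPT yields only a lower limit for CPT. A longer-lasting product undergoes more untreated-arm exposures before it fails, so its tests are more likely to be cut short.
- **Bias.** Kaplan-Meier can treat a stop as censoring only if stopping is unrelated to CPT. The regression of mean CPT has no provision for censored times. Entering a stop time as CPT pulls means down, and dropping the test loses data from a study of 7.

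If staff instead apply 10.2 selectively, the working rule is unwritten and, under the open design of Section 3, is applied by people who know the product.

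**Working it through.** **1. The plan's own figure.** Appendix 4 gives 7 participants for a 120 min difference at 80% power, with alpha 5% halved for two comparisons. No SD is stated. An SD of 68.9 min, solved backwards, reproduces all 30 cells of the two tables. With z(0.9875) = 2.241 and z(0.80) = 0.842, f = (2.241 + 0.842)² = 9.505, and n = 2 × 68.9² / 120² × 9.505 = 6.27, rounded up to 7. The textual conflict does not depend on this figure; it is used only in step 5.

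**2. Exposures before CPT.** With hourly exposures from time 0, a test with CPT of h hours has k = h + 1 untreated-arm exposures: 3 for 2 h, 7 for 6 h, 13 for 12 h. The minimum of 10 in Section 8.1 counts landings, not bites.

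**3. Share stopped by CPT.** Let p be the chance that one exposure produces an apparent reaction. Assume p is constant and exposures are independent. Then P(stopped) = 1 − (1 − p)^k.

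| p (assumed) | CPT 2 h, k = 3 | CPT 6 h, k = 7 | CPT 12 h, k = 13 |
|---|---|---|---|
| 1% | 3% | 7% | 12% |
| 5% | 14% | 30% | 49% |
| 10% | 27% | 52% | 75% |
| 20% | 49% | 79% | 95% |

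More than half of tests are stopped only if p exceeds 1 − 0.5^(1/k): about 21% (2 h), 9.4% (6 h) or 5.2% (12 h).

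**4. Effect of entering stop times as CPT.** Take two products with true CPTs of 4 h and 6 h, which is Appendix 4's 120 min difference. The mean recorded time is the sum of (1 − p)^i for i = 1 to h, so the recorded difference is (1 − p)^5 + (1 − p)^6 hours:

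- p = 1%: 0.951 + 0.941 = 1.892 h, or 114 min
- p = 5%: 0.774 + 0.735 = 1.509 h, or 91 min
- p = 10%: 0.590 + 0.531 = 1.122 h, or 67 min

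The longer-lasting product loses more, so the contrast shrinks.

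**5. Effect of dropping stopped tests.** Using the plan's formula and the back-solved SD, power = Φ(120 / (68.9 × √(2/n)) − 2.241). This gives 84.5% at n = 7, 72% with 25% of tests lost (n = 5.25) and 52% with 50% lost (n = 3.5). It is an illustration only: the formula is for independent groups, whereas each participant here tests all three products.

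**The case against.** The strongest reply is that the size of the problem is unknown and may be small. Section 3.2.1 says only that irritation may occur. Section 4.2 says volunteers are "chosen based on their insensitivity to the bites in order to limit any itchiness or discomfort", which lowers p by an unstated amount. At p = 1% only 3% to 12% of tests would stop. Reactivity also differs between people and the same 7 supply every test, so a constant p with independent exposures is a simplification. All of this stands.

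A reader might infer that the rule would end most tests, or that the median CPT could not be estimated. The documents support neither. They give no reaction rate and no expected CPT. Counting all 13 exposures overstates the risk for any test that reaches CPT earlier. Kaplan-Meier accepts censored times and can still give a median. A reader might also infer that the products differ in skin irritation and so in stops; Section 3.2.2 describes eye irritation for both actives and gives no skin comparison.

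Two further replies have partial force. Section 10.3 already records the time and counts of each exposure and adverse event monitoring, and Appendices 1 and 2 record relation to product, action taken, and exposure type and area. What is missing is an explicit stop reason and the arm involved. Section 10.2 may most naturally mean that the session ends, but it does not say so.

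That staff would not apply 10.2 literally is no answer: they would then be departing from the written rule.

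**Conclusion.** The conflict between Section 10.2 and Sections 3.2.1, 4.1 and 7.2.1 is established from the text, and no passage resolves it. The consequence is that an unknown, possibly large, share of tests could end before CPT. The range, from a few per cent to nearly all, depends on a reaction chance and a CPT that the documents do not give, and on the constant-p, independent-exposure assumption. The missing analysis rule matters whatever that share is, because the comparison of mean CPT in 9.2 cannot take a stopped test without bias or loss. Should-fix; confidence is high that the passages conflict and moderate on the impact.

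**What to change.** 1. The medically responsible person should reconcile Section 10.2 with 3.2.1, 4.1 and 7.2.1 so that they state one rule. No particular clinical rule is proposed here, and the reconciliation should not presume which way it goes. The text should say whether a stop ends the session or all participation, consistently with Section 4.4.
2. Add to the CRF an explicit stop reason and the arm involved. Exposure times are already captured.
3. In Section 9.2, treat a test stopped before CPT as censored at the last completed treated-arm exposure, not as a failure. Compare products with a method that accepts censored times and allows for repeated tests in the same participant. Align the synopsis.
4. Report the number, timing and reasons of stops by product beside the CPT result, so that a reader can judge whether stopping looks related to CPT.

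The cost is ethics committee review of the wording, a small CRF addition and a little more analysis work. No participants or visits are added.

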10.3. Data Monitoring

With the exception of the Volunteer Questionnaire, which is completed by the participant, all data collected will be recorded in the case report forms (CRF) and signed by the person completing the CRF. The CRF is considered to be source data.

Data to be collected are: Participant number and date of visit on every page, confirmation of informed consent, date of birth, eligibility details, bite test details (midge species, timing, 10 min and 72 h assessments), test visits (eligibility checklist, forearm measurement, product details, product application details, arm-in-cage testing data (time, fitness check, No. midges probing control arm, No. midges probing treated arm)) and adverse event monitoring.

Raw data from the CRF are then entered into an Excel spreadsheet for analysis and saved on the shared "i" drive (with access limited to members of the study team). Data will be double entered and verified to ensure accuracy. CRFs will be kept in locked storage.

Information in the database for each test will be linked to a relevant SOP, risk assessment, contract, and files of statistical analysis and location of report copy.

11. Regulatory Issues

11.1. Ethics approval

arctec will obtain approval from the LSHTM Ethics Committee for this trial. *arctec* will require a copy of the ethics approval letter before accepting participants into the study. The study will be conducted in accordance with the recommendations for physicians involved in research on human participants adopted by the 18th World Medical Assembly, Helsinki 1964 and later revisions.

11.2. Consent

Consent to enter the study must be sought from each volunteer only after a full explanation has been given, an information leaflet offered and time allowed for consideration. Signed volunteer consent should be obtained. The right of the participant to refuse to participate without giving reasons must be respected.

11.3. Confidentiality

Participants' identification data will be required for the enrolment process. The Trial Coordination Centre will preserve the confidentiality of participants taking part in the study and is registered under the Data Protection Act.

11.4. Sponsor

NEO-INNOVA HEALTHCARE LIMITED

11.5. Funding

NEO-INNOVA HEALTHCARE LIMITED will fund the study. Volunteers will be paid £60 per day (12 hour testing) to compensate for their time.

Appendix 1: Adverse Event Record Form

Study Title:

Volunteer number	reference	Date	Side effect/adverse event	Related to the product	Comments	Action taken
				Y/N/ don't know		

Appendix 2: Adverse Event Monitoring Questionnaire

[figure not shown]
To be completed by person who experienced the Adverse Event	
Name (first name SURNAME)	
Date of birth dd/mm/yyyy	
Phone number	
Mobile number	
E-mail address	
What kind of adverse event did you experience? e.g. skin rash, burning sensation, severe allergic reaction	
How long did the adverse event last?	
How serious was the event? mild / moderate / severe / life threatening	
Did you take any action to resolve the event?	
Was any treatment required?	
Did you visit A&E? Please enter details	
Did you stay in hospital overnight? Please enter details (no. nights/admission)	
Outcome unresolved / resolved / resolved with sequel	
To be completed by arctec trial manager	
Participant ID	
Study title	

Study code	
Type of study e.g. repellent, impregnated clothing, after-bite cream	
Exposure type e.g. chemical, mosquito bites, bed bug bites	
Exposure area e.g. forearm, legs	
Active ingredient	
Report date dd/mm/yyyy	
Other event Please enter details	
Likelihood of Adverse Event being related to study unrelated / unlikely / possible / probably / definite	
Serious Adverse Events	
Was the event serious? yes / no	
Admitted to Intensive Care Unit? yes / no	
Seriousness criteria (please tick)	
life threatening	
required hospitalisation	
prolonged hospitalisation	
congenital anomaly	

disabling/incapacitating	
important medical event	
required intervention to prevent impairment or damage	
Fatal	
If fatal, date of death dd/mm/yyyy	
Primary cause of death	
Was a post-mortem performed? yes / no	
Date adverse event become serious dd/mm/yyyy	
Possible contributing factors to SAE other than study participation or underlying disease being studied Please give details	
None apparent	
Concurrent illness, disease or other external factors	
Concurrent medication	
Study procedure	
Accident, trauma, or other external factors	
Other	
Relevant concomitant medication at time of SAE yes / no – if yes please provide details	
Treatments/procedures for SAE yes / no – if yes please provide details	

Relevant medical history (include only relevant past or concurrent medical disorder, surgeries, etc that might help explain the SAE)
 
yes / no – if yes please provide details
	

Relevant laboratory testing
 
yes / no – if yes please provide details
	

If relationship to study participation was unrelated, provide causality
 
Please give specific details
	
Discontinuation of study participation	
Concurrent disorder	
Concomitant medications	
Other	

If action taken with study participation, was study interrupted or discontinued?
 
Provide date (dd/mm/yyyy)
	

Did SAE abate after study was stopped?
 
yes / no / not applicable / unknown
	

Did SAE reoccur after reintroduction of study participation?
 
yes / no / not applicable / unknown
	

Narrative/Comments
 
Please describe the SAE including a chronological clinical presentation and evolution of the SAE and associated signs/symptoms
	

Please submit this questionnaire to [name]. SAEs that are assessed by the CI as being both related and unexpected must be reported to the LSHTM EC within 15 days of the CI becoming aware of the event.
	

Appendix 3: Flowchart for Safety Reporting

Appendix 4: Sample Size Calculation for a comparison trial between a positive control and two midge repellent products

A sample size calculation was done using CPT data from a previous study of a repellent against *Culicoides nubeculosus*. The sample size was calculated using the sample size formula for the comparison of 2 means with equal standard deviation. The required sample size per group is given by:

$$n = \frac{2\sigma^2}{\delta^2} f(\alpha, \beta)$$

Where δ^2 is the difference between the mean CPTs of 2 treatment groups, σ is the standard deviation of both treatment groups for one comparison which are assumed to be equal. $f(\alpha, \beta) = (z_{1-\alpha/2} + z_{1-\beta})^2$, which varied depending on the specified values of α and β .

Sample size calculation outcomes

The analysis revealed that for an experiment to compare mean CPT (in min) between any PMD products with Picaridin 20%, assuming a difference in mean CPT of 120 min, with a power of 80% and a significance level of 5%, 7 participants would be required.

A Bonferroni correction was applied for this analysis. The significance level at 5% ($\alpha = 0.05$) was divided by the number of comparisons being made to maintain overall significance level (here divided by 2, as 2 concentrations of PMD are being compared to Picaridin 20%).

Sample size calculation outcomes (with Bonferroni correction) when comparing between two PMD midge repellents and a Picaridin positive control.

Assumption of difference in mean CPT between any PMD group with Picaridin group (minutes)	Number of participants required per arm		
	Alpha = 5% Power = 70%	Alpha = 5% Power = 80%	Alpha = 5% Power = 90%
60	21	26	33
80	12	15	19
100	8	10	12
120	6	7	9
180	3	3	4

If only two arms are compared a Bonferroni correction would not be necessary and the numbers of participants needed for the study are slightly smaller.

Sample size calculation outcomes with the assumption of difference in mean CPT between one midge repellent and a Picaridin positive control.

Assumption of difference in mean CPT between PMD and Picaridin group (minutes)	Number of participants required per arm		
	Alpha = 5% Power = 70%	Alpha = 5% Power = 80%	Alpha = 5% Power = 90%
60	17	21	28
80	10	12	16
100	6	8	10
120	5	6	7
180	2	3	4

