Primary/Secondary Objective(s):	
Primary objective: To determine and compare the median complete protection time (CPT) of two insect repellent products and a positive control against Culicoides nubeculosus (midges).
 
Secondary objective: To determine and compare the protective efficacy of two insect repellent products and a positive control against Culicoides nubeculosus (midges).
		
Study Design / Methodology:	A single-centre laboratory setting study using healthy volunteers to test two insect repellent products (NEO-PART prolonged action release technology PMD (40% PMD) And NEO-PART prolonged action release technology PMD (35% PMD)) and a Positive control product (20% Picaridin, 'Smidge') against Culicoides nubeculosus midges.		
Number of Participants:	A total of 7 volunteers will be used to determine the median Complete Protection Time and protective efficacy of two insect repellents and a positive control against one midge species.		
Intended Product Users:	The test products are designed for use by the general public in areas where midge biting is likely.		
Study Duration:	
Participants will undergo a screening evaluation which includes a bite test (monitored for up to 72 hours), followed by up to 3 repellency tests of up to 12 hours duration. Each participant will be followed up after each visit by email/ in person/ by phone within 72 hours of the visit to monitor for adverse events. The minimum interval between the two repellency tests will be 72 hours. The minimum duration of participant involvement would therefore be approximately 3 weeks.
 
Total study duration (recruitment and participant involvement) is anticipated to be 1 month.
		

Inclusion Criteria:
	
 • Able and willing to give fully informed consent; • Able to understand and comply with the study procedures; • Consider themselves to be in good general health; • Male or female; • Aged 18 to 65 years; • Non-smokers or willing to refrain for 12 hours prior to and during each test; • Willing to undergo a bite test with Culicoides nubeculosus midges with up to 72 hour follow-up.

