APPENDIX 3: FLOWCHART FOR SAFETY REPORTING24

APPENDIX 4: SAMPLE SIZE CALCULATION FOR A COMPARISON TRIAL BETWEEN A POSITIVE CONTROL AND TWO MIDGE REPELLENT PRODUCTS.....25

1. Introduction

Mosquitoes, midges and other biting insects are vectors of extremely important diseases such as malaria, yellow fever, filariasis and many viruses and also may be of great nuisance value. The use of repellent products can provide added personal protection from disease transmission and nuisance bites. New effective repellents would offer an additional option for protection against biting insects. The tests carried out by *arctec* provide important information on the effectiveness of skin repellents, which will be used for label claims to accurately inform consumers and registration purposes.

The aim of this study is to determine the effectiveness of two topically applied insect repellent products provided by NEO-INNOVA HEALTHCARE LIMITED and one positive control containing the UK repellent brand 'Smidge'.

2. Objectives

Primary objective: To determine and compare the median complete protection time (CPT) of two insect repellent products and a positive control against *Culicoides nubeculosus* (midges).

Secondary objective: To determine and compare the protective efficacy of two insect repellent products and a positive control against *Culicoides nubeculosus* (midges).

3. Study Design

This is a single-centre, single-arm study with all participants testing two formulations containing PMD and a positive control product containing Picaridin. The control for each test is an untreated arm. There is no blinding or randomisation employed, since the outcome measures are based on midge behaviour. Repellent product testing takes place in a laboratory setting using 7 participants (preferably gender balanced). Each participant will test both PMD formulations and a positive control product (see section 8).

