9.1. Sample size calculation

Using data available from previous arm-in-cage repellent tests using midges, the power was determined for estimation of Complete Protection Times (CPT, primary outcome) at different values and standard deviations (Appendix 4). The sample size was calculated using the sample size formula for the comparison of 2 means with equal standard deviation. The required sample size per group was given by:

$$n = \frac{2\sigma^2}{\delta^2} f(\alpha, \beta)$$

Where δ^2 is the difference between the mean CPTs of 2 treatment groups, σ is the standard deviation of both treatment groups for one comparison which are assumed to be equal. $f(\alpha, \beta) = (z_{1-\alpha/2} + z_{1-\beta})^2$, which varied depending on the specified values of α and β .

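### The stated 80% power for 7 participants rests on normal quantiles for two independent groups; with t-based tests and no within-participant correlation it is about 72-78%

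*Combined protocol and SAP*

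**What the plan says.** Section 9.1 and Appendix 4 of the combined protocol and SAP size the trial with the "sample size formula for the comparison of 2 means with equal standard deviation". The printed formula is n = 2σ²/δ² × (z(1−α/2) + z(1−β))². It has no t correction and no correlation term. Appendix 4 describes σ only in words: it "is the standard deviation of both treatment groups for one comparison which are assumed to be equal". No value is given.

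Appendix 4 then concludes, "assuming a difference in mean CPT of 120 min", that "with a power of 80% and a significance level of 5%, 7 participants would be required". The 5% is split by Bonferroni ("here divided by 2, as 2 concentrations of PMD are being compared to Picaridin 20"%), so each comparison is sized at two-sided 0.025.

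The design is within-participant. The synopsis gives a total of 7 volunteers, and section 3 says: "Each participant will test both PMD formulations and a positive control product".

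On the analysis of mean CPT, section 9.2 plans a linear regression and allows for correlation within a participant only in a sensitivity analysis. The synopsis names a two-way ANOVA with Tukey's tests, or a general linear model.

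**The concern.** A normal-quantile formula treats the SD as known. Here it will be estimated from 21 observations at most, leaving 12 or 18 residual degrees of freedom, and at that size the t critical value is clearly larger than the normal one. The formula also treats the products as tested in separate groups of 7, whereas the same 7 people supply all the data. The first simplification overstates power. The second may understate it, but by an amount that the plan gives no means of judging.

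This power figure is the only justification given for 7 participants, and section 3.2.2 says that the results will inform product labelling. If the figure is too high, a non-significant comparison with Picaridin will be read with somewhat more confidence than it deserves.

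**Working it through.** **Inputs.** δ = 120 min, n = 7 per product, nominal power 80%, two-sided α = 0.05/2 = 0.025 (all Appendix 4). σ is not stated and has to be recovered from the tables.

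**Step 1: recover the SD.** Assume each of the 30 table cells is the formula's result rounded up. Two cells set the limits:
- Corrected table, 60 min, 80% power, n = 26: the unrounded n must exceed 25, so σ > 60 × √(25 / (2 × 9.505)) = 68.81.
- Uncorrected table, 100 min, 90% power, n = 10: the unrounded n is at most 10, so σ ≤ 100 × √(10 / (2 × 10.507)) = 68.98.

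All 30 cells are reproduced for σ between 68.81 and 68.98 min. I use 68.9.

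**Step 2: reproduce the plan's figure.** n = 2 × 68.9² / 120² × (2.241 + 0.842)² = 0.6593 × 9.505 = 6.27, rounded up to 7. This agrees with Appendix 4. Because of the rounding, the normal formula at n = 7 gives more than 80%: SE = 68.9 × √(2/7) = 36.83, 120/36.83 = 3.258, and Φ(3.258 − 2.241) = 84.5%.

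**Step 3: replace the normal distribution with the t.** The inputs are unchanged, the correlation is zero and the noncentrality is 3.258.

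| Analysis | Residual df | Critical value | Power |
|---|---|---|---|
| Regression on three products (section 9.2) | 21 − 3 = 18 | 2.445 | 78.4% |
| Two-sample t-test (the formula's own setting) | 14 − 2 = 12 | 2.560 | 74.8% |
| Product + participant model | 21 − 3 − 6 = 12 | 2.560 | 74.8% |
| Two-way ANOVA with Tukey's tests (synopsis) | 12 | 3.773/√2 = 2.668 | 71.6% |

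The Tukey row uses Tukey's own family-wise 5% critical value for three products, and takes the two factors to be product and participant, which the synopsis does not spell out. Across the SD range in step 1, the 18 df figure is 78.3-78.5% and the 12 df figure 74.7-74.9%.

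The difference detectable with 80% power at α = 0.025 is 122 min with 18 df and 127 min with 12 df.

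**Step 4: allow for correlation ρ between a participant's CPTs.** The SE of a product difference becomes σ√(2(1 − ρ)/n).
- Product + participant model, 12 df: at ρ = 0.11, SE = 68.9 × √(2 × 0.89/7) = 34.74, noncentrality 3.454, power 80.0%. At ρ = 0.2 and 0.3 it is 84% and 89%.
- Tukey with 12 df: 71.6% at ρ = 0, 81.8% at 0.2 and 87.0% at 0.3. It passes 80% between 0.15 and 0.2.
- Regression without a participant term, 18 df, by simulation: about 80% at ρ = 0.15, 80.5% at 0.2 and 84% at 0.5. Power rises slowly because the residual variance still contains the between-participant part.

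**Step 5: dependence on alpha.** At 0.05 per comparison and ρ = 0, power is 84.8% (12 df) or 86.9% (18 df).

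**The case against.** The case for leaving the text alone has real substance.

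- *The arithmetic is right.* The 7 and all 30 cells follow from the printed formula, and its z quantiles are visible. This stands: the fault is the choice of approximation at single-digit n, not a miscalculation.
- *For the regression in section 9.2 the gap is 1.6 points, or 2 min of detectable difference*, while CPT is read at hourly tests with a half-hour confirmation. This stands as to size. The synopsis, however, names a different analysis with a larger gap, and the plan does not say which governs.
- *Section 9.2 states no alpha and no Bonferroni correction; at 0.05 power exceeds 80%.* The figures are correct. But the 80% claim in Appendix 4 is made for the corrected level, so that is where it has to hold.
- *Pairing may make up the shortfall.* It may, since a modest ρ is enough. But the plan states no ρ, its formula uses none, and the section 9.2 regression names no participant term.
- *The primary endpoint is median CPT by Kaplan-Meier, which this calculation does not address.* True, but the sample size is justified on mean CPT and the products are to be compared on mean CPT, so the figure is still relied on.

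A reader might infer that the trial is underpowered. The documents do not support that: with the correlation unknown, true power may lie on either side of 80%.

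**Conclusion.** The stated 80% is not met on the plan's own independent-groups assumption once the SD is treated as estimated. At n = 7, 120 min and α = 0.025, power is about 78% for the section 9.2 regression and 75% with 12 df. It is 72% for the synopsis's Tukey comparison at its family-wise 5%. The shortfall is 2 to 8 points, smallest for the analysis in the main text.

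This rests on three assumptions: the SD of 68.9 min recovered from the tables, the corrected alpha, and zero within-participant correlation. It disappears at a correlation of about 0.11 in the product + participant model, or about 0.15-0.2 in the regression without a participant term and for Tukey with 12 df.

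Two stronger inferences should be resisted. One is that an eighth participant is required. Eight would give 82.2% (14 df) or 84.8% (21 df) at zero correlation, but a restated power, or a justified correlation, serves equally well with 7. The other is that the 180 min table rows, where n is only 2 to 4, show a serious failure. The approximation is weakest there, but those rows did not set the sample size.

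**What to change.** In section 9.1 and Appendix 4:

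1. State the SD used (about 68.9 min, if the recovered value is right) and that it comes from the earlier study of a repellent against the same midge species.
2. Replace the 80% claim with, for example: 7 participants give about 75-78% power for a 120 min difference in mean CPT at two-sided alpha 0.025 if CPTs within a participant are uncorrelated. Alternatively, give the difference detectable with 80% power as about 122-127 min.
3. Choose one model for comparing mean CPT, so that the synopsis and section 9.2 agree. Report t-based power for that model with its assumed within-participant correlation and its alpha. If Tukey's tests are kept, the zero-correlation figure to report is about 72%.

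The cost is a few sentences and a slightly less favourable power figure. No extra participants are needed and conduct of the trial does not change.
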